We hypothesize that preterm infants supplemented with early physiologic doses of L-carnitine while on parenteral nutrition will have improved short-term growth parameters and significantly higher neurobehavioral scores when compared with control infants.

Primary Aims:

To determine whether carnitine supplementation is associated with:

- 1. Decreased percent weight loss within the first two weeks of life and decreased length of time to regain birthweight.
- 2. Improved performance on the NICU Network Neurobehavioral Scale (NNNS) at 40 weeks postmenstrual age (+/- 2 weeks).

Secondary Aims:

To determine whether carnitine supplementation is associated with:

- 1. Increased rate of growth of head circumference within the first month of life and increased food efficiency (weight gain/calorie intake) during the supplementation period.
- 2. Normalization of the serum carnitine profile at two weeks of life, compared with infants born at a post-menstrual age 2 weeks later.
- 3. Enhanced brain maturation as measured by amplitude-integrated EEG (aEEG) measurements obtained during the hospital course
- 4. Fewer abnormal findings, better brain growth, white matter development and brain metabolism on brain magnetic resonance imaging (MRI) at 36-40 weeks' corrected age (prior to hospital discharge)

Because of the potential for systemic effects of L-carnitine supplementation, we will also monitor those variables which showed significant difference in our prior study: rates of proven infection, hearing screen failure and PDA ligation.

Primary Outcomes:

- 1. Length of time to regain birthweight,
- 2. Percent weight loss in the first two weeks of life,
- 3. Neurodevelopmental scores on the NICU Network Neurobehavioral Scale (NNNS) at 40 weeks post-menstrual age (+/- 2 weeks)

Methods/Design:

This is a prospective, randomized controlled clinical trial involving infants with gestational age (GA) <32 wks who are born at either the Jack D. Weiler Hospital or the Wakefield Division of Montefiore and admitted to theirNeonatal Intensive Care Unit. Informed consent will be obtained from the parents of eligible patients as early as possible within 72 hours of birth. Infants whose parents have signed an informed consent form will be randomized to receive either carnitine supplementation (50 µmol/kg/day) versus placebo within 72-96 hours of birth.

Inclusion criteria:

- Infants born <32weeks' gestation
- Exclusion criteria:
 - Presence of

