 - o potentially life-threatening congenital anomaly
 - o known hereditary metabolic disorder
 - o known chromosomal abnormality
 - teratogen exposure with symptomatic substance withdrawal
 - o congenital viral infections
 - microcephaly
 - Grade IV intraventricular hemorrhage (IVH) or seizures documented within first 72 hours of birth
 - Critically-ill with life expectancy less than 72 hours
 - Unable to obtain consent within 72 hours of birth
 - Enrolled in another intervention trial

Participant recruitment: Parents or guardians of infants who meet study criteria will be approached regarding the study as early as possible within 72 hours of the infant's birth. Informed consent will be obtained by study investigators and coordinators. Permission will be requested to re-contact the families after completion of the supplementation study for follow-up.

Randomization: As previously described by Pande et al., enrolled patients will be randomized to either the treatment group (L-carnitine, 50 µmol/kg/day) or placebo group (5% glucose, similar volume as the L-carnitine group).²⁸ Patients who meet study entry criteria and have signed informed parental/guardian consent will be enrolled in the study. Because gestational age and small for gestational age (SGA) status will impact our outcome measures, we will ensure they are equally distributed in the arms of the study by stratifying based upon these variables. We will analyze the two study arms using an intent-to-treat analysis. Therefore, enrolled patients will be stratified into fourgroups: gestational age 23 to 26 6/7 weeks, gestational age 27 to 29 6/7weeks, gestational age 30 to 31 6/7 weeks and small for gestational age (SGA). Patients within each stratum will be randomized by the pharmacist using a computerized block-generation with sets of 4. In the case of multiple births, all infants must meet study criteria, and the infants will be randomized as a set. One infant of the multiple-birth set will be randomly chosen for inclusion in the analysis. A recruitment log of all screened infants will be maintained. Clinicians and the nursing staff will be unaware of the arm of the treatment protocol to which the patient is assigned. Codes will be unblinded only after all patients have reached the study end-point, or at the request of the Data Safety Monitoring Board.

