- 1. Patient demographics: date of birth, birth weight, gestational age as determined by best obstetric estimate or Ballard score, SGA or LGA status, Apgar scores, birth history, delivery room management, gender, ethnicity.
- 2. Maternal characteristics: maternal age, maternal language, ethnicity, presence of prenatal care, type of insurance coverage, maternal educational status, presence of maternal depression, teratogen exposure (alcohol, tobacco or illicit drug use during pregnancy), antenatal steroid use, hypertension/pre-ecclampsia, gestational diabetes/Type I or II diabetes, and maternal infections.
- 3. Management of fluid and nutrition: daily fluid intake and urine output, glucose infusion rate, total caloric intake, total protein intake, and food efficiency (weight gain divided by caloric intake) while on study supplement.
- 4. Hospital course:
 - a. Growth parameters: weight, length and head circumference at birth, daily weight until birthweight regained and then weekly, weekly length, and head circumference two times per week for four weeks)
 - b. Cardiovascular: need for vasopressors, presence of PDA (including medical or surgical treatment; platelet count and mean fluid intake at time of treatment)
 - c. Gastrointestinal: feeding intolerance, NEC, presence of gastrointestinal reflux,
 - Neurological: results of aEEG readings, results of head ultrasounds including presence of germinal matrix/intraventricular hemorrhage and periventricular leukomalacia, cranial MRI results
 - e. Opthalmological: grade of retinopathy of prematurity and treatment or ophthalmologic diagnosis,
 - f. Hematologic: transfusion history including dates
 - g. Infectious disease: presence of concurrent presumed and proven infection,
 - h. Other: performance of any surgical procedures, duration of intravenous access, use of medications, and hearing screen results (OAE and/or ABR) with observed thresholds of hearing frequencies.
 - i. Clinical Risk Index for Babies (CRIB) scores will be calculated for each infant.
 - j. We will also monitor for possible short-term side effects.
- 5. Discharge information: weight, length, head circumference, and diagnoses at time of discharge, routinely-ordered discharge brain MRI findings
- 6. Neurodevelopmental assessment:

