We will assess neurodevelopmental outcomes at 18-24 months corrected age using the Bayley Scales of Infant and Toddler Development, Third Edition (BSID-III). The BSID-III is a validated instrument used for assessing the development of Cognitive, Language (Receptive and Expressive), Motor (Fine and Gross), Social-Emotional and Adaptive skills in infants and toddlers. This normative assessment yields scaled scores, composite scores, percentile ranks, and developmental age equivalents, all of which provide important information about a child's level of functioning relative to his or her same-age peers. While Cognitive, Language and Motor skills are assessed through direct interaction with the child, Social-Emotional and Adaptive skills are obtained from parent report. Because the BSID-III is commonly used for identifying children who are in need of early intervention due to developmental delays, this instrument will be sensitive to detecting the types of developmental issues we often see in very young children born preterm. Additionally, at the follow-up visit at 18-24 months corrected age, we will administer two parental questionnaires: the Modified Checklist for Autism in Toddlers (M-CHAT) and the Child Behavior Checklist (CBCL). M-CHAT is a parent-report checklist developed to screen children for early signs of autistic features. The CBCL is a standardized, well-validated parent-report questionnaire developed to assess various maladaptive behavioral and emotional problems in young children.

Record confidentiality: Records relating to the study will be kept in a secure location, to which only study personnel will have access. Records will be kept in a locked file cabinet in the neonatology offices and in a password-protected computer.

Statistical Analyses:

Statistical analysis will be performed with the assistance of a statistician.

Sample size:

We plan to recruit a total of 150 infants for our study over approximately 36months' time. This number is based upon an expected attrition of approximately 50 infants over the course of the study and a desired sample size of 100 infants. The inclusion of 100 infants in our study (50 in each study arm) will allow us to detect a moderate difference in our primary outcomes at a significance level of 0.05 with a power of 0.8. (0.5 SD; α = .05; power = .80).

Primary Outcomes	Mean	Standard Deviation	0.5 x Standard Deviation
Percent weight loss*	10.8%	6.2	3.1
Time to regain	11.3 days	4.3	2.2
birthweight*			

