The effect of L-carnitine supplementation on outcome measures in enrolled infants will be examined for significance by comparing the two groups using unpaired data analysis with the assistance of a statistician. Continuous data (percent weight loss, time to regain birthweight, NNNS score, BSID-III scores) will be compared between the "placebo" and the "carnitine supplemented" groups by unpaired student t-test (a 2 tailed P value <0.05 will be considered to indicate statistical significance) or Wilcoxon's rank sum test for non-parametric parameters. Unmatched nominal data will be compared using Fisher's Exact Test or Chi-square test as required (e.g.: presence or absence of normalization of the carnitine profile; or presence or absence of pathological findings on the discharge MRI). Logistic regression models will be used to adjust for potentially confounding factors including gestational age, birth weight, race, gender, Apgar scores.

Risks and Discomforts:

A brief description of the risks and discomforts associated with this study is included in the protocol consent form and will be discussed in detail with each family at the time of study enrollment.

Carnitine is routinely administered with parenteral nutrition in approximately one-third of the neonatal intensive care units in the United States, although not in the Jack D. Weiler Hospital or Montefiore North Division NICU's. Carnitine is FDA-approved, and there have been no reports of severe toxicity from

overdose. Data available from the adult literature reports side effects of mild gastrointestinal symptoms such as gastritis, vomiting, diarrhea or abdominal cramping; body odor; and seizures, in patients with or without a known seizure disorder. These side effects are dose-dependent and might be avoided by slow consumption of the solution or greater dilution. One investigator reported transient elevation of triglycerides and increased platelet aggregation in uremic patients with severe renal insufficiency who received high doses of carnitine supplementation.⁵²

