There is a theoretical risk of reduced closure of patent ductus arteriosus (PDA) in infants treated with indomethacin who receive carnitine supplementation as opposed to placebo.²⁸ In our previous study, an increase in PDA ligation among infants treated with indomethacin was seen. The observation may have been due to chance. It is also possible that an interaction between carnitine and indomethacin occurred. Indomethacin enhances the process of apoptosis, which mediates PDA closure.⁵³ Carnitine has been shown to reduce apoptosis in such models as ischemia-reperfusion injury.⁵⁴ However, it should also be noted that the group of carnitine-supplemented infants with the increased rate of PDA ligation had lower birthweight and had received more fluids prior to intervention, compared to the infants in the placebo group. Increased fluid intake has been shown to be associated with failure of medical management of PDA.⁵⁵If this effect was in fact associated with decreased apoptosis, it reinforces our hypothesis regarding neuronal protection, a benefit we feel outweighs a theoretical risk of reduced PDA closure.

Despite this incidental finding, there have been no other reports of adverse effects in neonates receiving supplementation doses (approximately 50 µmol/kg/day) although approximately one-third of NICU's in the United States supplement carnitine routinely in parenteral nutrition. In addition, there have been at least 13 clinical trials of carnitine in premature infants which did not report side effects.

We have established a Data and Safety Monitoring Board. The DSMB will meet approximately every 6 months to review safety data. Meetings will be convened via conference calls. Emergency meetings may be convened at any time by the board in the event that questions/concerns regarding patient safety have been raised or if an unexpected AE/SAE occurs that is possibly related to the study. A report will be circulated to the board members approximately 2 weeks before the board meeting in order to provide them with adequate time to review the materials.

Infants in our study will be monitored closely in order to detect unforeseen side effects. All AEs will be collected and recorded as part of the study. For each, the PI will include the following assessments:

- Anticipated/unanticipated
- Relationship to the study intervention
- Outcome

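### Does time to regain birthweight need a written rule for infants who die before regaining it?

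*Combined protocol and SAP*

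**What the plan says.** Primary Aim 1 and the Primary Outcomes list both name "length of time to regain birthweight". The Randomization section adds: "We will analyze the two study arms using an intent-to-treat analysis". Under Outcome Measures, the effect of carnitine "on outcome measures in enrolled infants will be examined for significance". That section goes on: "Continuous data (percent weight loss, time to regain birthweight, NNNS score, BSID-III scores) will be compared between" the two groups, with a two-tailed t-test or the "rank sum test for non-parametric parameters".

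The Sample size section allows for "an expected attrition of approximately 50 infants over the course of the study and a desired sample size of 100 infants". It does not split those losses by cause or timing. The growth items under Data collection specify "daily weight until birthweight regained and then weekly", with no last day. Risks and Discomforts gives 2010 unit mortality of about 75% at 23 weeks, 24% at 24-26 weeks and 5% at 27-29 weeks, and expects similar rates in the trial. It also states: "All AEs will be collected and recorded as part of the study".

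No section excludes, ranks, censors or imputes an infant who dies or leaves before regaining birthweight. The one mention of survivors, under Neurodevelopmental assessment, concerns the 40-week visit.

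**The concern.** Both planned tests need a number for each infant. An infant who dies on day 8, still below birthweight, has none. A strict reading of intent-to-treat says that this infant must be counted, yet the named tests cannot count the infant without a rule.

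Two rules are defensible. One leaves such infants out and compares those who regained birthweight. The other ranks death before regain as the worst result. They answer slightly different questions and can fall on opposite sides of 5%. If the choice waited until after unblinding, it could be made to suit the result. If early deaths differed by arm, leaving them out could also flatter the arm that lost more of its sickest infants. The plan itself expects substantial mortality in the least mature infants, so the case is not hypothetical.

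**Working it through.** **1. The plan's own sizing.** 150 recruited less 50 lost leaves 100, or 50 per arm; 50/150 = 33%. The target is 0.5 SD = 0.5 × 4.3 = 2.15 days. The t-based power at 50 per arm is 0.70 two-sided and 0.80 one-sided, so the stated 0.80 is met only one-sided. That is a separate matter, and nothing here depends on it. What counts here is that 50 per arm is the number left after losses. This fits an analysis of infants with an observed value.

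**2. How many infants are affected (assumed; the documents give no count).** Apply the stated mortality to two assumed case mixes, with no deaths counted at 30-31 weeks because no rate is given.
- Lower mix (20% at 24-26 weeks, 30% at 27-29): 150 × (0.20 × 0.24 + 0.30 × 0.05) = 9.5 deaths.
- Higher mix (5% at 23 weeks, 35% at 24-26, 30% at 27-29): 150 × (0.05 × 0.75 + 0.35 × 0.24 + 0.30 × 0.05) = 20.5 deaths.

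These cover the whole stay. If a quarter to a half precede regain, the range is 0.25 × 9.5 = 2.4 to 0.5 × 20.5 = 10.2 infants, or about 2% to 7% of 150. The window is short: supplementation starts by 72-96 hours and mean regain is at 11.3 days, so about 7 to 8 days. Infants with life expectancy under 72 hours are excluded.

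**3. Bias from leaving deaths out.** Model: the frailest fraction q of an arm is lost before regain, and frailty has correlation r with time to regain (r is assumed). With φ the normal density and z_q the upper-q normal point, let h(q) = φ(z_q)/(1 − q). Loss then lowers an arm's observed mean by 4.3 × r × h(q). Here h(0.02) = 0.049, h(0.05) = 0.109 and h(0.10) = 0.195.

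| Loss by arm | r = 0.3 | r = 0.5 |
|---|---|---|
| equal | 0 | 0 |
| 5% v 2% | 0.08 days (0.02 SD) | 0.13 days (0.03 SD) |
| 10% v 2% (extreme) | 0.19 days (0.04 SD) | 0.31 days (0.07 SD) |

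For scale, the standard error of the difference at 75 per arm is 4.3 × √(2/75) = 0.70 days. The 5% v 2% bias is at most 0.13/0.70 = 0.18 standard errors, and 0.13/2.15 = 6% of the target difference.

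**4. Does the rule change the verdict?** Simulation with r = 0.4, times normal with mean 11.3 and SD 4.3 in whole days (floor at day 4), equal loss by arm and a true difference of 2.15 days. The rank sum test is run with deaths left out and with deaths ranked last.

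| | 2% lost per arm | 5% lost per arm |
|---|---|---|
| Rules disagree, 50 per arm | 8% | 13% |
| Rules disagree, 75 per arm | 5% | 11% |
| Purely random loss changes the verdict, 50 per arm | 3% | 7% |

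On identical data, the t-test and rank sum test themselves disagree in about 5% of trials at 50 per arm. About half of the disagreement between the rules is therefore ordinary borderline instability at a power near 0.67. With no true effect, taking the better of the two death rules gives 6% to 7% false positives; taking the better of the two tests already named in the plan gives about 6%.

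**5. Power.** With 2% lost in the treated arm and 10% in placebo, t-test power from 50 per arm is about 0.56, against 0.67 with equal 5% loss. That start removes deaths from a number already net of attrition. From the 75 recruited per arm, the contrast is about 0.73 to 0.75 against 0.84 to 0.85. Siblings not chosen for analysis reduce the 75 by an unstated number.

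**The case for a change.** The strongest case for a change is that it would cost only a few sentences and would close a choice on a primary outcome before unblinding. An unqualified intent-to-treat statement does not match a comparison limited to infants who regained birthweight. This much stands: the text is silent, and the label is loose.

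The choice also matters more when losses differ by arm. With a true difference of 2.15 days, 50 per arm and random loss of 10% treated against 5% placebo, rank sum power is about 0.64 with deaths left out and 0.36 with deaths ranked last. With those losses reversed it is 0.65 and 0.71. But this gap arises because ranking deaths last makes the test partly a comparison of mortality. It does not show that the planned comparison of time to regain is wrong. With no effect on time and losses of 10% v 2%, the test with deaths ranked last rejects about 8% of the time, against 6% to 7% for the t-test. Under equal 5% loss its power is 0.58, against 0.65 with deaths left out. It is not a better primary analysis.

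Two cautions apply to the reassurance as well. That equal loss causes no bias, and that the arm losing more looks faster, are properties of the model. Treatment could change which infants die, and no section says that infants who die would have regained birthweight later.

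**Conclusion.** No change to the plan follows. This is missing detail that an analyst would fill sensibly: compare infants with an observed time, in the arm assigned, as the sizing from 150 to 100 implies. Daily weighing until regain makes the t-test or rank sum test legitimate for infants who survive and stay. Stratification by gestational age spreads the risk of death across the arms. Adverse events are recorded with their outcome, so early deaths can be counted by arm and read beside the result.

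The likely distortion is small: nil with equal loss, 0.02 to 0.03 SD with 5% v 2%, and at most 0.07 SD in the extreme 10% v 2% case. These sizes rest on assumed early deaths (about 2 to 10 of 150), assumed correlations of 0.3 to 0.5 between frailty and time to regain, and an unstratified model. A clear imbalance in deaths before regain would call for caution in reading this outcome, whichever rule was used.

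### The 18-24-month BSID-III scores are compared without adjustment for the randomisation strata or for maternal education, so precision available from data already collected goes unused

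*Combined protocol and SAP*

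**What the plan says.** All references are to the combined protocol and SAP.

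- **Outcome Measures (Statistical Analyses).** "Continuous data (percent weight loss, time to regain birthweight, NNNS score, BSID-III scores) will be compared between the" placebo and carnitine "groups by unpaired student t-test", with Wilcoxon's rank sum test as the alternative. The criterion is that "a 2 tailed P value <0.05 will be considered to indicate statistical significance". Neither test takes covariates.
- **Same paragraph, adjustment.** Logistic regression is planned for possible confounders. The list is open-ended and names gestational age, birth weight, race, gender and Apgar scores. The sentence does not say which outcomes it covers. No linear model or analysis of covariance appears anywhere.
- **Randomization.** Allocation is stratified into four groups: three gestational-age bands and SGA. The stated reason is that these factors affect the outcomes.
- **Data collection, item 2.** The maternal data include "presence of prenatal care, type of insurance coverage, maternal educational status, presence of maternal depression".
- **Data collection, item 4.i.** "Clinical Risk Index for Babies (CRIB) scores will be calculated for each infant". This item stands under the hospital course, and no scoring time is given.
- **Primary Outcomes and Secondary Aims.** BSID-III is in neither list. It is a scheduled follow-up assessment at 18-24 months corrected age.
- **Sample size.** "The inclusion of 100 infants in our study (50 in each study arm") is the evaluable target, after an "expected attrition of approximately 50 infants over the course of the study". The stated basis is "0.5 SD; α = .05; power = .80", for the primary outcomes only.

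**The concern.** The plan names gestational age and SGA as prognostic, uses them to stratify, and then compares the arms as if they had not been used. The adjustment sentence shows that the authors intended some covariate analysis, but the model they named cannot be fitted to a BSID-III composite. So no stated adjusted analysis exists for these scores. Maternal education, a characteristic that precedes treatment, is collected but used in no analysis.

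What is at stake is the width of the interval on the arm difference. At 18-24 months, BSID-III is the only instrument that includes direct testing of the child; M-CHAT and CBCL are parent report. About 100 infants are expected to remain, so there is little precision to spare. In addition, the covariates for continuous outcomes stay open to choice after results are known, because the adjuster list is not closed.

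**Working it through.** **Inputs from the documents:** 50 infants per arm, 0.5 SD difference, alpha 0.05 (Sample size); two-sided test (Outcome Measures); four strata (Randomization). The documents give no SD or target difference for BSID-III, so 0.5 SD is borrowed from the primary outcomes.

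**Assumed:** R², the share of BSID-III variance explained by the covariates together, taken as 0.05 to 0.20.

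**1. The plan's own figure.** In SD units the standard error of the difference is √(2/50) = 0.20, so the noncentrality is 0.5/0.20 = 2.5. The t-test then has power 0.799 at one-sided 0.05 and 0.697 at two-sided 0.05. The stated 0.80 therefore reproduces only one-sided. Under the two-sided test that the plan specifies, the starting point is about 0.70. Attrition reproduces: 100/(1 − 1/3) = 150.

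**2. Effect of adjustment.** A linear model reduces the residual SD by the factor √(1 − R²). The standard error becomes 0.20 × √(1 − R²), the noncentrality becomes 2.5/√(1 − R²), and the equivalent gain in infants is 1/(1 − R²) − 1. Stratum (3 df), maternal education as a single term (1 df) and sex (1 df) leave 100 − 2 − 5 = 93 residual degrees of freedom.

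| R² (assumed) | Standard error (SD) | Equivalent extra infants | Power, two-sided 0.05 |
|---|---|---|---|
| 0 (t-test) | 0.200 | – | 0.70 |
| 0.05 | 0.195 | 5.3% | 0.72 |
| 0.10 | 0.190 | 11.1% | 0.74 |
| 0.15 | 0.184 | 17.6% | 0.77 |
| 0.20 | 0.179 | 25.0% | 0.79 |

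The interval narrows by 1 − √(1 − R²), which is about 2.5% at R² = 0.05 and about 10.6% at 0.20.

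**3. Cost in degrees of freedom.** At R² = 0.20, power is 0.7903 with 98 residual degrees of freedom and 0.7899 with 93. The loss is negligible.

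**4. A refinement for the strata.** Stratified allocation already balances the strata, so the true spread of the unadjusted difference is smaller than the t-test's standard error implies. In the extreme case where all of R² = 0.20 comes from perfectly balanced strata, the unadjusted test has power Φ((0.5 − 1.96 × 0.20)/0.179) = Φ(0.60) ≈ 0.73 by normal approximation. The adjusted analysis has 0.798 on the same scale. The gain is then about 7 points instead of 9. It comes from using a standard error that matches the design.

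**The case against.** The strongest case against has five parts.

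- **The unadjusted test is valid.** This stands. A reader might infer that a chance imbalance in maternal education would appear as a treatment effect. Under randomisation the comparison is unbiased and its standard error already allows for such imbalance. As an illustration, a 10-point imbalance with a 0.6 SD score gap (both assumed) shifts the difference by 0.10 × 0.6 = 0.06 SD, or 0.06/0.20 = 0.3 standard errors.
- **The prognostic claim is not documented.** This stands for maternal education: the documents say nothing about its relation to BSID-III. It does not stand for the strata, which the protocol itself calls influential.
- **CRIB is not shown to be a baseline variable.** This stands. A reader might want CRIB to replace Apgar scores as an adjuster. CRIB is listed under the hospital course without a scoring time, Apgar scores are listed with the birth data, and nothing in the documents ranks one above the other.
- **Adjustment is already intended.** The sentence shows the intent and a statistician is to assist, but a logistic model does not fit these scores, so the gap remains.
- **The outcome is minor and the gain may be small.** BSID-III is neither primary nor a listed secondary aim and has no power calculation. At R² = 0.05, losing about 5% of infants to missing maternal education in a complete-case model would cancel the gain. The maternal interview has no fixed visit. This limits the importance of the point but does not remove it.

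**Conclusion.** The point holds as a question of efficiency. The only stated methods that fit the BSID-III scores are unadjusted, and the one adjusted model does not fit them. The result is a wider interval than the collected data require.

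The gain is roughly 2 to 9 power points at 50 per arm, and somewhat less where the explained variance comes from strata already balanced by design. It rests on an assumed R² of 0.05-0.20 and a borrowed 0.5 SD target. The documents do not support reading this as bias, as an invalid test or as a flaw in a primary analysis. The sponsor should make the change because it costs almost nothing and replaces a stated method with a more precise one.

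**What to change.** Before unblinding, amend the Outcome Measures text as follows.

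1. Analyse each BSID-III score by a linear model with arm, randomisation stratum (four levels), maternal education (years or ordered category) and sex. Report the adjusted difference with its 95% confidence interval. The t-test or rank sum test can remain as a supporting analysis.
2. Limit the logistic regression sentence to binary outcomes and close its list of covariates.
3. State how missing maternal education will be handled, so that infants are not dropped for a missing covariate.
4. Keep CRIB out of the model unless it is confirmed to be scored before the study supplement starts.

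The cost is wording only. Stratum is known from randomisation, and maternal education and sex are already on the case report form. The small downsides are five degrees of freedom and the missing-data rule.
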